2 STUDY DESCRIPTION

2.1 Study design

CA209-9TM was a randomized, double-blinded, placebo-controlled, phase 3 study of nivolumab or nivolumab plus cisplatin, in combination with radiotherapy in subjects with cisplatin ineligible and cisplatin eligible locally advanced squamous cell carcinoma of the head and neck (LAD SCCHN).

As of 15-Oct-2018, enrollment into the study was closed. At implementation of Revised Protocol 03, the study will be unblinded and placebo treatments will no longer be given. All enrolled subjects must be re-consented prior to continuing treatment on the study.

The study consists of two independent cohorts:

- **Cohort 1** will randomize subjects who are ineligible for cisplatin chemotherapy to receive nivolumab in combination with radiotherapy (**Arm A**) or cetuximab in combination with radiotherapy (**Arm B**).
- **Cohort 2** will randomize subjects who are eligible to receive cisplatin-based therapy to receive nivolumab in combination with cisplatin and radiotherapy (**Arm C**) or cisplatin and radiotherapy (**Arm D**).

In each cohort subjects will be randomized to the two treatment arms in a 1:1 ratio and stratified

by risk group (intermediate vs. high), PD-L1 tumor expression ($\geq 1\%$ vs. $< 1\%$ or indeterminate), and ECOG PS (0 vs. 1).

Cohort 1 (cisplatin ineligible):

[figure not shown]
- **Arm A** subjects will be administered Nivolumab in combination with intensity-modulated radiation therapy (IMRT).
 1. Nivolumab 240 mg single dose will be administered at w1d1 followed by 360 mg every 3 weeks for a total of 3 doses starting at w3d1 followed by 480 mg every 4 weeks for a total of 6 doses.
 2. IMRT 70 Gy will be administered as 35 fractions starting from w3d1 over 7 weeks.
- **Arm B** subjects will be administered cetuximab in combination with IMRT.
 1. cetuximab 400 mg/m² single dose will be administered at w2d1 followed by 250 mg/m² every week for a total of 7 doses starting at w3d1.
 2. IMRT 70 Gy will be administered as 35 fractions starting from w3d1 over 7 weeks.

Cohort 2 (cisplatin eligible):

- **Arm C** subjects will be administered Nivolumab in combination with Cisplatin and IMRT.
 1. Nivolumab 240 mg single dose will be administered at w1d1 followed by 360 mg every 3 weeks for a total of 3 doses starting at w3d1 followed by 480 mg every 4 weeks for a total of 6 doses.
 2. Cisplatin 100 mg/m² will be administered every 21 days starting at w3d1 for a total of 3 doses.
 3. IMRT 70 Gy will be administered as 35 fractions starting from w3d1 over 7 weeks.
- **Arm D** subjects will be administered Cisplatin and IMRT.
 1. Cisplatin 100 mg/m² will be administered every 21 days starting at w3d1 for a total of 3 doses.
 2. IMRT 70 Gy will be administered as 35 fractions starting from w3d1 over 7 weeks.

[figure not shown]
The current study design schematic after unblinding is presented in [Table 2.1-1](#)

Table 2.1-1: Study Design Schematic

The original study design schematic is presented in Table 2.1-2

Table 2.1-2: Original Study Design Schematic

2.2 Treatment assignment

After protocol specific informed consent is signed subject will be registered into the Interactive Response Technology (IRT). Randomization begins with call to IRT, in order to be randomized to a treatment subject must have an evaluable PD-L1 and HPV p16 result from the central lab.

In each of the two cohorts subjects will be randomized in 1:1 ratio using three stratification factors:

- Risk group (intermediate vs. high).
- PD-L1 tumor expression ($\geq 1\%$ vs. $< 1\%$ or indeterminate),
- ECOG PS (0 vs. 1).

As of 15-Oct-2018 and Per revised protocol 03, the following are effective:

- Enrollment for new subjects is closed, the IRT system is closed to enroll new patients.
- Subjects who have signed an informed consent as of 15-Oct-2018 and are currently undergoing screening procedures, may be permitted to be randomized to the study.
- Subjects currently being treated in the study will have the option to continue treatment under the Revised Protocol 03. These subjects will be re-consented by signing a revised informed consent document.

2.3 Blinding and Unblinding

Per original design CA209-9TM was a double-blind placebo-controlled study. Per Revised Protocol 03 and as of 15-Oct-2018 study will be unblinded, placebo treatment removed.

2.4 Protocol Amendments

Table 2.4-1: Protocol Revision History

Document	Date of Issue	Summary of change
Original Protocol	15-Aug-2017	Not applicable
Revised Protocol 01	01-Nov-2017	Update to questionnaire administration updated to align with dosing cycles. Outcome research assessment and endpoints redefined updated to align with analysis planned. TNM Staging clarified for high and intermediate risk definition. Other minor corrections, clarifications.
Revised Protocol 02	21-Feb-2018	Added exclusion of subjects with active interstitial lung disease (ILD) / pneumonitis or with a history of ILD / pneumonitis requiring steroids. Aligned thyroid testing to study visits. Added guidance for premedications for cetuximab if necessary.
Revised Protocol 03	16-Nov-2018	Enrollment in the study was closed as of 15-Oct-2018. Revised Protocol 03 covers the changes implemented to the protocol post study enrollment closure: study treatment unblinding, removal of placebo treatment, and removal of analysis of efficacy end-points and efficacy follow-up.

3 OBJECTIVES

Not Applicable per Revised Protocol 03.

4 ENDPOINTS

4.1 Safety Endpoints

The assessment of safety will be based on the incidence of adverse events (AEs), serious adverse events (SAEs), adverse events leading to discontinuation, adverse events leading to dose modification, select adverse events (select AEs), immune-mediated AEs (IMAEs), time to onset and time to resolution of immune-related AEs, and deaths. In addition, clinical laboratory tests will be analyzed.

5 STUDY PERIODS, TREATMENT REGIMENS AND POPULATIONS FOR ANALYSES

5.1 Study Periods

- Baseline period:
 - Baseline evaluations or pre-treatment events will be defined as evaluations or events that occur before the date and time of the first dose of study treatment.
Evaluations on the same date and time of the first dose of study treatment will be considered baseline evaluations.
Events (AEs) on the same date and time of the first dose of study treatment will not be considered as pre-treatment events.
 - In cases where the time (onset time of event or evaluation time and dosing time) is missing or not collected, the following definitions will apply:
 - ◆ Pre-treatment AEs will be defined as AEs with an onset date prior to but not including the day of the first dose of study treatment;
 - ◆ Baseline evaluations will be defined as evaluations with a date on or prior to the day of first dose of study treatment.
 - If there are multiple valid observations on or prior to the first dose of study treatment, then the latest non missing observation on or before first dose date (and time if collected) will be used as the baseline in the analyses. If multiple observations exist on the latest collection date (and time if collected), the record with the latest data entry date and time will be used. If multiple observations exist on the latest collection date (and time if collected) and data entry date and time, then the first observation is used as baseline, unless otherwise specified.
 - ◆ For Eastern Cooperative Oncology Group (ECOG) performance status (PS), the latest ECOG PS value prior to or on the first dose date (and time if collected) will be used as the baseline in the analyses. If multiple records fall on the last date then the record with the highest value of ECOG PS will be considered as baseline.
 - ◆ For PD-L1, among the records prior to or on first dose date (and time if collected), identify first those with quantifiable test result. If there are no records with quantifiable test result, then select those with indeterminant result ("INDETERMINATE"). If there

are no records with indeterminant test result, then select those with unavailable result ('NOT EVALUABLE). If there are no records with unavailable test result, then select those with not reported or not available result (all other records). The latest record will be used as the baseline in the analyses. If there is more than one record for the latest date, then choose the one with the greatest specimen ID.

- Post baseline period:
 - On-treatment AEs will be defined as AEs with an onset date and time on or after the date and time of the first dose of study treatment (or with an onset date on or after the day of first dose of study treatment if time is not collected or is missing). For subjects who are off study treatment, AEs will be included if event occurred within a safety window of 30 days (or 100 days depending on the analysis) after the last dose of study treatment. No "subtracting rule" will be applied when an AE occurs both pre-treatment and post-treatment with the same preferred term and grade.
 - On-treatment evaluations (laboratory tests, pulse oximetry and vital signs) will be defined as evaluations taken after the day (and time, if collected and not missing) of first dose of study treatment. For subjects who are off study treatment, evaluations should be within a safety window of 30 days (or 100 days depending on the analysis) after the last dose of study treatment.
- For subjects who are off study treatment safety assessments will only be collected through 100 days post last dose.

5.2 Treatment Regimens

Treatment group "as randomized" corresponds to the treatment group assigned by the Interactive Response Technology (IRT) system.

Treatment group "as treated" will be same as the treatment group "as randomized" by IRT unless a subject received the incorrect study treatment for the entire period of treatment, in which case the subject's treatment group "as treated" will be defined as the incorrect study treatment.

All analyses will be performed using the treatment group "as randomized", except for dosing and safety for which analyses will be performed using treatment group "as treated".

All analyses for cisplatin ineligible cohort and cisplatin eligible cohort will be presented separately unless specified otherwise.

5.3 Populations for Analyses

- Enrolled subjects: All subjects who signed the informed consent no later than 15-Oct-2018.
- Randomized subjects: All enrolled subjects as defined above who were randomized through the IRT.
- Treated subjects: All randomized subjects who received at least one dose of any study drug (Nivolumab, Nivolumab-Placebo, Cetuximab, Cetuximab-Placebo, Cisplatin).

6 SAMPLE SIZE AND POWER

Per Revised Protocol 03, sample size will be limited to the patients enrolled as of October 15, 2018. Accordingly no efficacy analyses will be performed and no power is considered.

7 STATISTICAL ANALYSES

7.1 General Methods

Unless otherwise noted, discrete variables will be tabulated by the frequency and proportion of subjects falling into each category, grouped by treatment. Percentages given in these tables will be rounded to the first decimal and, therefore, may not always sum to 100%. Percentages less than 0.1 will be indicated as ‘< 0.1’. Continuous variables will be summarized by treatment group using the mean, standard deviation, median, minimum, and maximum values.

The conventions to be used for imputing missing and partial dates for analyses requiring dates are described in [Section 8](#).

Analyses will be performed for each cohort separately.

7.1.1 *Adverse Events, Serious Adverse Events, Multiple events, Select Adverse Events, Other Events of Special Interest and Immune-Mediated Adverse Events*

Drug-related AEs are those events with relationship to study drug “Related”, as recorded on the CRF. If the relationship to study drug is missing, the AE will be considered as drug-related.

Serious adverse events consist of AEs deemed serious by the Investigator and flagged accordingly in the CRF and clinical database.

Adverse events leading to study drug discontinuation are AEs with action taken regarding study drug(s) = “Drug was discontinued”.

Adverse events leading to dose delay are AEs with action taken regarding study drug(s) = “Drug was delayed”.

Adverse events leading to dose reduction are AEs with action taken regarding study drug(s) = “Dose was reduced”.

Adverse events will be coded using the Medical Dictionary for Regulatory Activities (MedDRA), and the most recent version of the dictionary at the time of the database lock will be used. Adverse event results will be graded for severity using the NCI Common Terminology Criteria for Adverse Events (CTCAE) and the version of the criteria specified in the protocol will be used.

In the AE summary tables, unless otherwise specified, subjects will be counted only once at the Preferred Term (PT), only once at the System Organ Class (SOC), and only once at subject level for the counting of total number of subjects with an AE. The AE tables will be sorted by the SOCs and then PTs. SOC will be ordered by descending frequency overall and then alphabetically. PTs will be ordered within SOC by descending frequency overall and then alphabetically. The sorting

will be done based on the ‘Any Grade’ column of the experimental arm when arms are presented side-by-side.

Unless otherwise specified, the AE summary tables will be restricted to on-treatment events regardless of the causality.

Analyses that take into account the multiple occurrences of a given adverse event will be conducted (see [Section 7.6.9](#)). To prepare these analyses, the CRF data will be processed according to standard BMS algorithms¹ in order to collapse adverse event records into unique records based on the preferred term. These data will be presented as the rate per 100 person-years of exposure. These analyses will take into account all on-treatment events (allowing more than 1 event per subject) and the total exposure time. The person-year exposure will be computed as the sum over the subjects’ exposure expressed in years where the exposure time is defined as

- (Date of last dose of study treatment - date of first dose of study treatment + 31 days (or 101 days, depending on the analysis))/365.25, for subject who are off study treatment and were followed for at least 30 days (or 100 days, depending on the analysis) after last dose of study treatment. Exposure time calculation will be based on all study therapy including administration of placebo drugs.
- (Last known alive date - date of first dose of study treatment +1)/365.25, for subjects who are still on-treatment or who are off study treatment and were followed less than 30 days (or 100 days depending on the analysis) after last dose of study treatment.

7.1.1.1 Select Adverse Events

The select Adverse Events (select AEs) consist of a list of preferred terms grouped by specific category. AEs that may differ from or be more severe than AEs caused by non-immunotherapies and AEs whose early recognition and management may mitigate severe toxicity are included as select AEs. Categories of select AEs may include subcategories.

The list of MedDRA preferred terms used to identify select adverse events is revisited quarterly and updated accordingly. The preferred terms used for the selection at the time of the database lock will be provided by categories/subcategories.

In addition to the frequency and worst severity of select AEs, time-to onset, time-to resolution, and time-to resolution where immune modulating medication was initiated will be analyzed for each specific category/subcategory of drug-related select AEs when applicable.

7.1.1.2 Other Events of Special Interest

Other events of special interest (OEOSI) consist of a list of preferred terms grouped by specific category. The list of MedDRA preferred terms used to identify OEOSI is revisited quarterly and updated accordingly. The preferred terms used for the selection at the time of the database lock by categories will be provided.

7.1.1.3 *Immune-Mediated Adverse Events*

In order to further characterize AEs of special clinical interest, analysis of immune-mediated AEs (IMAE) will be conducted. IMAEs are specific events (or groups of PTs describing specific events) considered as potential immune-mediated events by investigator that meet the definition summarized below:

- those occurring within 100 days of the last dose,
- regardless of causality,
- treated with immune-modulating medication (of note, endocrine AEs are considered IMAEs regardless of immune-modulating medication use, since endocrine drug reactions are often managed without immune-modulating medication).
- with no clear alternate etiology based on investigator assessment, or with an immune-mediated component

The list of MedDRA preferred terms used to identify IMAEs is revisited quarterly and updated accordingly. The preferred terms used for the selection at the time of the database lock by categories will be provided.

7.1.2 *Laboratory Tests*

Clinical laboratory parameters (hematology, serum chemistry and electrolytes) will be evaluated.

Laboratory tests will be graded using the NCI Common Terminology Criteria, and the most recent version of the criteria at the time of the database lock will be used.

Clinical laboratory data will be analyzed using International System of Units (SI) and repeated using US conventional units.

In the laboratory summary tables, unless otherwise specified, subjects will be counted only once for each lab parameter according to their worst on treatment CTC grade (worst being the highest CTC grade). The laboratory tables and listings will be sorted by laboratory category, laboratory subcategory and laboratory test code sequence number.

7.2 *Study Conduct*

7.2.1 *Accrual*

By subject listing of informed consent (and re-consent if available), randomization date, first dosing date, country, investigational site will be provided.

7.2.2 *Relevant Protocol Deviations*

Not Applicable.

7.3 *Study Population*

Analyses in this section will be tabulated for all randomized subjects by treatment group as randomized, unless otherwise specified. Analyses will be performed separately for cisplatin ineligible and cisplatin eligible cohorts.

7.3.1 *Subject Disposition*

Number of subjects who discontinued study treatment along with corresponding reason will be tabulated by treatment group as treated. Reason for discontinuation will be derived from subject status CRF page. This analysis will be performed only on the all treated subjects population.

A by-subject listing for all treated subjects will be provided showing the subject's off treatment date and whether the subject continue in the treatment period/study along with the reason for going off treatment period/study.

7.3.2 *Demographics and Other Baseline Disease Characteristics*

The following demographic and baseline disease characteristics will be summarized and listed by treatment group as randomized:

- Age (continuous)
- Age categorization (< 65, ≥ 65 and < 75, ≥ 75 and < 85, ≥ 85, ≥ 75, ≥ 65)
- Sex (Male vs. Female)
- Race (White, Black or African American, Asian, Other)
- Asian race subgroups (Asian Indian, Chinese, Japanese, Korean, Taiwanese, Malay, Other Asian)
- Ethnicity (Hispanic/Latino and Not Hispanic/Latino) *

* Required for US subjects only

- Region (US/Canada, Europe, Asia, Rest of the World)
- ECOG PS (0 vs. 1 vs. >1)
- CNS metastasis at Baseline (Yes, No) - per radiographic tumour screening assessment
- Smoking Status (Current/Former, Never, Unknown)
- Smoking History (<= 20 pack year history vs. > 20 pack year history)
- PD-L1 (>=1%, <1%, indeterminate, non-evaluable)
- Creatinine clearance (< 60mL/min vs. >= 60mL/min)

Creatinine clearance is estimated by Cockcroft-Gault formula:

$$CCr = \{((140 \text{ age in years}) \times \text{weight in Kg}) / (72 \times \text{serum creatinine in mg/dL})\}$$

(for females, multiply the result by 0.85)

- Disease stage at initial diagnosis (stage III, IV)
- TNM Classification at initial diagnosis
- Time from Initial Disease Diagnosis to Randomization (< 1 year, 1 - < 2 year, 2 - < 3 year, 3 - < 4 year, 4 - < 5 year, ≥ 5 year).
- SCCHN risk of tumor recurrence (Intermediate vs High).
- Sites of diseases (all lesions) at baseline per Investigator
- Number of disease sites per subject (all lesions) at baseline per Investigator
- Number of target lesions, non-target lesions and disease sites at baseline per Investigator
- Tumor burden: sum of the diameters of target lesions at baseline per Investigator

A listing of randomization scheme presenting randomized treatment group and as treated treatment group will be provided for all randomized subjects.

7.3.3 *Medical History*

Not Applicable.

7.3.4 *Prior Therapy Agents*

Prior systemic cancer therapy, prior radiotherapy, and prior surgery will be summarized by treatment group and overall and listed by subject.

7.3.5 *Physical Examinations*

Not Applicable.

7.3.6 *Baseline Physical Measurements*

Not Applicable.

7.4 *Extent of Exposure*

Analyses will be performed by treatment group “as treated”. Listings will include all available exposure data.

7.4.1 *Administration of Study Therapy*

A by-subject listing of study drug dosing will be provided.

7.4.2 *Modifications of Study Therapy*

No additional analysis will be provided.

7.4.2.1 *Dose Delays*

Each Nivolumab, Cetuximab, and Cisplatin infusion including corresponding placebo drugs may be delayed. A dose will be considered as actually delayed if the delay is exceeding 3 days (i.e. greater than or equal to 4 days from scheduled dosing date). Reason for dose delay will be retrieved from CRF dosing pages.

7.4.2.2 *Infusion Interruptions and Rate Changes*

Each Nivolumab, Cetuximab, and Cisplatin infusion including corresponding placebo drugs may be interrupted and/or the IV infusion rate can be reduced. This information will be retrieved from CRF dosing pages.

7.4.2.3 *Dose Escalations*

Dose escalations are not allowed for any of the study drug.

7.4.2.4 *Dose Reductions*

Nivolumab dose reductions are not allowed.

Cetuximab and Cisplatin dose may be reduced up to two times, need for further reduction will require drug discontinuation. Once a dose has been decreased, it should remain reduced for all

subsequent dosing unless dose is further reduced. Dose reduction information will be retrieved from CRF dosing pages.

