7.4.3.2 Subsequent Cancer Therapy

Not Applicable.

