7.6.6 Select Adverse Events

Analyses will be performed by select AE category.

7.6.6.1 *Incidence of Select AE*

Select AEs will be summarized by treatment group for each category/subcategory.

The following analyses will be conducted using the 30-day safety window only:

- Overall summaries of any select AEs by worst CTC grade (any grade, grade 3-4, grade 5) presented by Category or Subcategory/PT.
- Overall summaries of any drug-related select AEs by worst CTC grade (any grade, grade 3-4, grade 5) presented by Category or Subcategory/PT.

A by-subject select AE listing will be provided.

7.6.6.2 *Time-to Onset of Select AE*

Not Applicable.

7.6.6.3 *Time-to Resolution of Select AE*

Not Applicable.

7.6.7 *Immune-Mediated Adverse Events*

IMAEs will be summarized by treatment group for each immune-mediated category / PT using the 100-day safety window:

- Overall summary of non-endocrine IMAEs by worst CTC grade (any grade, grade 3-4, grade 5) where immune modulating medication was initiated presented by Category / PT.
- Overall summary of endocrine IMAEs by worst CTC grade (any grade, grade 3-4, grade 5) presented by Category / PT.

A by-subject listing of IMAEs will be provided. By-subject listings of time-to resolution for longest IMAEs cluster (any grade and grade 3-5 in separate summaries) will also be provided.

7.6.8 *Other Events of Special Interest*

A by-subject listing of OEOSI will be provided.

7.6.9 *Multiple Events*

Not applicable.

7.6.10 *Laboratory Parameters*

The analysis population for each laboratory test is restricted to treated subjects who underwent that laboratory test. Laboratory tests (in addition to the tests specified below) with CTC criteria collected in the specific studies may also be included in the summaries.

7.6.10.1 *Hematology*

The following will be summarized by treatment group as worst CTC grade on-treatment per subject and as shift table of worst on-treatment CTC grade compared to baseline CTC grade per

subject: hemoglobin (HB), platelets, white blood counts (WBC), absolute neutrophils count (ANC) and lymphocyte count (LYMPH).

The analyses will be conducted using the 30-day safety window.

A by-subject listing of these laboratory parameters will be provided.

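### The 100-day IMAE summaries neither cut nor flag events starting after subsequent anticancer therapy, so toxicity from an off-study checkpoint inhibitor could be counted under the study arm

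*SAP*

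**What the plan says.** **Window.** SAP Section 5.1 states that, for subjects off study treatment, "AEs will be included if event occurred within a safety window of 30 days (or 100 days depending on the analysis", counted from the last dose of study treatment. Section 7.1.1.3 restricts IMAEs to "those occurring within 100 days of the last dose". Neither section gives any other end point.

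**Definition.** Section 7.1.1.3 sets several conditions:
- The event belongs to a specified event or group of preferred terms that the investigator considers potentially immune-mediated.
- It falls in the window.
- It counts "regardless of causality".
- It was treated with immune-modulating medication, except that "endocrine AEs are considered IMAEs regardless of immune-modulating medication use".
- It is an event "with no clear alternate etiology based on investigator assessment, or with an immune-mediated component".

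**Tabulation.** Section 7.6.7 says "IMAEs will be summarized by treatment group for each immune-mediated category / PT using the 100-day safety window", with separate summaries for non-endocrine and endocrine events. Section 7.6 groups subjects as treated, and Section 5.2 defines that by study treatment alone. The adverse event summaries in Sections 7.6.2 to 7.6.6 all use 30 days.

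**Later therapy.** Section 7.4.3.2, "Subsequent Cancer Therapy", is marked Not Applicable.

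**Setting.** Under Revised Protocol 03, "the study will be unblinded and placebo treatments will no longer be given" (Section 2.1). Section 2.2 makes continuing on study optional and subject to re-consent.

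**The concern.** A 100-day window is long enough for a subject to stop study treatment, start another cancer drug and have a reaction to it. If that drug is a checkpoint inhibitor, the reaction resembles the toxicity the IMAE tables are meant to describe. Nothing in the rule separates the two sources.

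The matter is sharpest in arms B and D. Their subjects were not assigned nivolumab and learned this at unblinding. An IMAE from an off-study drug in one of them would raise the control rate and shrink the apparent excess in arm A or C. No output planned in the SAP names the later drug or its start date, so a reader of the report could not tell.

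**Working it through.** The SAP gives no IMAE rate, arm size or rate of subsequent therapy, so it has no figure to reproduce. The check has three parts: the logic of the rule, the dates implied by the schedule, and an illustration on assumed inputs.

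**1. Does the rule exclude the event?** Take an IMAE that the investigator attributes to an off-study checkpoint inhibitor.

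| Condition (Section 7.1.1.3) | Met? |
|---|---|
| Specified event, potentially immune-mediated per investigator | Plausibly yes |
| Within 100 days of last study dose | Depends on dates |
| Causality | Not a filter |
| Immune-modulating medication | Needed if non-endocrine; not needed if endocrine |
| No clear alternate etiology | No |
| **or** an immune-mediated component | Yes |

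The last two rows are alternatives within one bullet. Failing the first does not exclude the event, because the second is satisfied. All the other conditions must still hold.

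**2. How much of the control window is free of study drug?** Take w1d1 as day 1, so w2d1 is day 8 and w3d1 is day 15 (Section 2.1).
- Cisplatin, every 21 days for 3 doses: days 15, 36, 57.
- Cetuximab: day 8, then 7 weekly doses from day 15, the last on 15 + 6 × 7 = day 57.
- Last scheduled active control dose: day 57 in both arms.
- The 30-day window ends on day 57 + 30 = 87. The 100-day window ends on day 57 + 100 = 157.

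With placebo removed, days 58 to 157 contain no scheduled study drug for a control subject who completes the schedule, yet all of them count for IMAEs.

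**3. Illustration.** Every input here is an assumption, not an SAP figure. Let f be the share of a control arm starting an off-study checkpoint inhibitor in the window (5-20%). Let q be the chance that such a subject then has a qualifying IMAE (10-30%).

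The rise in the control rate is at most f × q, reached when no affected subject already counts:
- low: 0.05 × 0.10 = 0.5 points
- high: 0.20 × 0.30 = 6.0 points

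The chance of at least one such subject among n is 1 - (1 - fq)^n:

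| n per arm (assumed) | Low (fq = 0.005) | High (fq = 0.06) | Shift from one subject |
|---|---|---|---|
| 10 | 4.9% | 46.1% | 10 points |
| 25 | 11.8% | 78.7% | 4 points |
| 50 | 22.2% | 95.5% | 2 points |

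For the effect on the contrast, assume also true rates of 20% with nivolumab and 5% in control, and independence of the two sources.
- **Control arm only affected.** Control rate = 5% + 95% × fq = 5.475% to 10.7%. The difference falls from 15.0 to 14.5 (low) or 9.3 points (high). The ratio falls from 4.0 to 20/5.475 = 3.65 or 20/10.7 = 1.87.
- **Both arms affected equally.** The difference is (20 - 5) × (1 - fq) = 14.9 (low) or 14.1 points (high).

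The result therefore depends mainly on how unequal later therapy is between arms. The SAP gives no information on that.

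**The case against.** The strongest case on the other side is that a fixed window without regard to causality is a legitimate choice, because it avoids attribution judgments. A hard cut at new therapy could also drop delayed nivolumab events in arms A and C and bias the comparison the other way. This stands, and it is why the uncut table should remain the main one.

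A reader might infer more than the text supports in three ways:
- **That any event with an immune-mediated component qualifies.** It does not. That phrase is half of one bullet, the other conditions still apply, and non-endocrine events need immune-modulating medication. The SAP also calls its list a summary of the definition.
- **That control-arm rates are in fact inflated and nivolumab will look safer than it is.** No section says that any subject received an off-study checkpoint inhibitor. Unblinding and optional continuation make it possible, not established. The same uncut window applies to arms A and C, so a one-directional effect is an assumption.
- **That these tables are the main or only evidence on immune toxicity.** Select adverse events, all and drug-related, are summarized over 30 days (Section 7.6.6.1). An event attributed only to an off-study drug should not be recorded as related to study drug. Objectives are Not Applicable, no power is considered, and no test depends on the IMAE tables.

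The planned listings of IMAEs, dosing and off-treatment dates might let a reader compare onset with last dose, but none is specified to show later therapy. Feasibility is a fair question, since Revised Protocol 03 removed efficacy follow-up (Section 2.4). However, the IMAE rule already needs medication data through the 100-day window, and Section 8 already handles non-study medication dates.

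**Conclusion.** The point holds as a conditional gap in the rule. If a subject started an off-study checkpoint inhibitor within 100 days of the last study dose and had an event meeting the remaining IMAE conditions, the SAP would tabulate it under the study arm with nothing to mark it. In arm B or D this would narrow the apparent IMAE difference. In arm A or C it would add to the nivolumab rate.

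The size cannot be derived from the document. The illustrated range, from negligible to several points, rests wholly on assumed start rates, event risks and arm sizes. The effect is confined to descriptive tables and listings. This is a worthwhile, inexpensive clarification, not an error that undermines the safety analysis.

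**What to change.** Keep the 100-day IMAE tables in Section 7.6.7 as the main result and add two items there:
1. In the IMAE listing, flag any event with onset on or after the first subsequent systemic anticancer therapy and give the drug class, using the non-study medication or subsequent therapy data where collected.
2. Provide one supplementary IMAE table by treatment group that excludes the flagged events, to be read beside the main tables.

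If the data do not capture later therapy for some subjects, say so in a footnote.

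The cost is SAP wording, one derived date and one extra table. The supplementary table may leave out some delayed nivolumab events, so it should not replace the uncut version.
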